10. STATISTICAL CONSIDERATIONS

Before database lock, a statistical analysis plan will be issued as a separate document, providing detailed methods for the analyses outlined below. Any deviations from the planned analyses will be described and justified in the clinical study report.

The baseline value of any variable will be defined as the last available value prior to the first administration of study drug (ESK-001 or placebo). A patient is considered randomized into the study following treatment assignment by IxRS.

All statistical tests will be two-sided. Except where noted, evaluation of continuous variables will be performed using ANOVA; ANOVA will be replaced by the nonparametric counterpart if normality assumptions are severely violated. Between-group comparisons involving discrete data will be performed using contingency table methodology. Descriptive summaries of continuous data will present the group mean, SD, median, range, and sample size. Descriptive summaries of discrete data will report the number of patients and incidence as a frequency and as a percentage. Statistical comparisons will be performed at the 0.05 level of significance.

10.1. Analysis of the Conduct of the Study

The disposition of patients will be summarized by treatment group with respect to the number of patients randomized, treated, and completing the study. For patients who discontinue treatment early, reasons for discontinuation will be summarized by treatment group.

Important Protocol Deviations (IPD) will be summarized. ICH E3 defines important protocol deviations as a subset of protocol deviations that may significantly impact the completeness, accuracy, and/or reliability of the study data or that may significantly affect a subject's rights, safety, or well-being.

10.2. Analysis of Treatment Group Comparability

Demographics (age, sex, race/ethnicity) and baseline characteristics (e.g., duration of psoriasis, psoriasis severity at baseline, baseline PASI) will be summarized by treatment group.

10.3. Efficacy Analyses

Efficacy analyses will be based on the intent-to-treat (ITT) approach. All patients randomized (ITT population) will be included in the analysis, and subjects will be analyzed according to their randomized treatment. Unless otherwise noted, analyses of efficacy outcome measures will be stratified by prior use of biologics and geographic region.

10.3.1. Primary Efficacy Endpoint

The proportion of patients in the active treatment groups with $\geq 75\%$ improvement in PASI at Week 12 relative to baseline will be compared between each treatment group and placebo using the Cochran-Mantel-Haenszel test adjusting for stratification factors.

10.3.2. Secondary Efficacy Endpoints

Similar analyses as in the primary efficacy analyses will be performed to compare any two active arms.

The proportion of patients in each treatment group and placebo with sPGA categories 0 or 1 (cleared or minimal) at Week 12 will be compared using the Cochran-Mantel-Haenszel test adjusting for stratification factors.

The proportion of patients in each treatment group and placebo with response rate in PASI-50, 90, and 100 at Week 12 relative to baseline will be compared using methods similar to those used for PASI-75.

Change in percent BSA at Week 12 relative to baseline will be performed using ANOVA or analogous nonparametric methods.

Change from baseline in DLQI at Week 12 relative to baseline will be performed using ANOVA or analogous nonparametric methods.

The proportion of patients in each treatment group and placebo with $\geq 75\%$ improvement in PASI Week 12 relative to baseline will be compared using the Cochran-Mantel-Haenszel test adjusting for stratification factors.

No adjustments for multiplicity will be performed.

Graphical methods may be used to display efficacy data.

10.3.3. Exploratory Endpoints

- Change from baseline in pruritus NRS score at Week 12 will be performed using ANOVA or analogous nonparametric methods.
- Change from baseline in EQ-5D at Week 12 will be performed using ANOVA or analogous nonparametric methods.
- Change from baseline in psoriasis and TYK2-related skin biomarkers in response to ESK-001 treatment.
- Change from baseline in psoriasis and TYK2-related blood-based biomarkers in response to ESK-001 treatment.
- Change from baseline in transcriptomic and proteomic expression in response to ESK-001 treatment.

Exploratory PD endpoint analyses may not be included in the CSR.

10.4. Safety Analyses

Safety will be assessed through the summary of adverse events, serious adverse events, laboratory test results, ECG parameters, and vital signs. Safety analyses will include all subjects who receive at least one dose of either ESK-001 or placebo. Subjects will be analyzed according to the actual treatment received.

Patient deaths (if any) will be listed.

10.4.1. Adverse Events

Verbatim descriptions of treatment-emergent adverse events will be mapped to thesaurus terms using the Medical Dictionary for Regulatory Activities (MedDRA). Adverse events will be tabulated by body system and preferred term. Summaries of adverse events by severity will be provided. Adverse events judged by the investigator to be related to treatment (ESK-001 or placebo) will be prepared. Serious adverse events will be summarized similarly. Adverse events leading to discontinuation from the study or treatment will be listed and tabulated.

10.4.2. Laboratory Tests

Descriptive summaries of laboratory values, including changes from baseline and treatment-emergent abnormalities, will be generated. Shift tables reflecting changes from baseline (e.g., normal to low, high) will be presented for a subset of laboratory parameters.

The liver function tests, namely ALT, AST, ALP, and TBL, are used to assess possible drug-induced liver toxicity (DILI). A listing of liver function test results that meet DILI criteria will be generated.

10.4.3. 12-Lead Electrocardiogram

The RR, PR, QRS, and QT intervals will be measured and read by a central laboratory. HR will be calculated as $60 / (\text{RR} \times 1000)$ (with RR expressed in msec) and rounded to the nearest integer.

Correction for Heart Rate

Corrected QT interval (QTc) will be calculated using the manually over-read QT values. Each individual ECG QT value will be corrected for HR. The measured QT data will be corrected for HR using QTcF as per the following formulae/method (with QT, RR and QTc expressed in msec):

Fridericia's Correction:

$$QTcF = \frac{QT}{(RR / 1000)^{(1/3)}}$$

ECG Numeric Variables

HR, PR, QRS, and QTcF will be summarized using descriptive statistics. For each time point of measurement, the changes from baseline will be summarized using descriptive statistics.

Categorical Analysis

The incidence count and percentage of patients with any postdose QTcF values of >450 msec, >480 msec, and >500 msec will be tabulated. Patients with QTcF values >520 msec will be listed with corresponding baseline values, Δ QTcF, and baseline and treatment HR. The incidence count and percentage of patients with Δ QTcF increase from baseline of >30 msec and >60 msec will be tabulated.

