8.3.3. Vital Signs

Vital signs will be assessed at the time points detailed in the Schedule of Assessments (see [Section 1.3](#)). The following vital signs will be measured:

- Blood pressure (systolic and diastolic [mmHg])
- Heart rate (bpm)
- Body temperature (°C)

BP and heart rate recordings will be made after the patient has been resting supine or semi-recumbent for ≥ 5 minutes.

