8.1 Adverse Events

AEs will be coded to MedDRA version 25.0. AEs will be presented by SOC and PT, unless otherwise noted, in order of descending frequency on the overall total, and multiple occurrences of the same event in the same participant will be counted only once in the tables.

The following summaries of AEs will be provided:

- Overall summary of TEAEs
- All TEAEs
- Study drug related TEAE
- TEAEs by severity
- Grade 3 or higher TEAE
- Serious TEAEs (SAEs)
- Study drug-related SAEs
- TEAE leading to treatment discontinuation
- TEAE leading to death

By-subject listings of all AEs, SAEs, TEAEs leading to treatment discontinuation, TEAE leading to death will also be provided.

8.2 12-lead Electrocardiogram

12-lead electrocardiogram (ECG) data will be measured and read by local and central laboratory, and will be summarized for all subjects in the Safety Analysis Population.

8.2.1 *ECG Numeric Variables*

HR, PR, QRS, and Fridericia-corrected QT (QTcF) interval based on central ECG read and changes from baseline will be summarized by treatment group using descriptive statistics. The change from baseline of these ECG parameters at each time point will be listed for each subject.

8.2.2 *Categorical Analysis*

The number and percentage of subjects with maximum treatment-emergent post-dose QTcF values based on central ECG read in the following mutually exclusive categories will be summarized by treatment group: > 450 msec, > 480 msec, > 500 msec, > 520 msec, and > 550 msec. The number and percentage of subjects with maximum post-dose QTcF increase from baseline of > 30 msec and > 60 msec (mutually exclusive) will be summarized by treatment group.

Clinical significance will be summarized by treatment group and overall for the local and central ECG reads separately.

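### The protocol's ECG heart-rate formula, 60/(RR × 1000) with RR in msec, returns 0 bpm for every possible ECG; it should be 60/(RR/1000)

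*Protocol*

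**What the plan says.** Protocol 10.4.3 (12-Lead Electrocardiogram) first sets out what the central laboratory supplies: "The RR, PR, QRS, and QT intervals will be measured and read by a central laboratory". Heart rate is not among these measured quantities. It is derived: "HR will be calculated as $60 / (\text{RR} \times 1000)$ (with RR expressed in msec) and rounded to the nearest integer". The closing words, "with RR expressed in msec) and rounded to the nearest integer", fix both the unit and the rounding rule, so neither is left to interpretation.

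The Fridericia correction follows in the same section. It uses the same unit ("with QT, RR and QTc expressed in msec") but divides RR by 1000 before taking the cube root.

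The derived heart rate has two uses in that section. It is summarized at each time point together with its change from baseline ("HR, PR, QRS, and QTcF will be summarized using descriptive statistics"). It also appears in the listing of patients with QTcF above 520 msec, which shows "and baseline and treatment HR".

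SAP 8.2.1 (ECG Numeric Variables) keeps heart rate beside PR, QRS and the QTcF "interval based on central ECG read and changes from baseline will be summarized by treatment group using descriptive statistics". It gives no heart-rate formula. SAP section 12, the place for changes from protocol-defined analyses, shows no correction in the public text.

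**The concern.** With RR in milliseconds, the interval in seconds is RR/1000, and beats per minute is 60 divided by that. The protocol has multiplication where division is needed, so the two formulas in one section convert the same variable, in the same unit, in opposite directions.

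ECG heart rate is a planned safety variable. A programmer who follows the protocol literally gets 0 for every patient, visit and arm, and a change from baseline of 0 throughout. A programmer who corrects it without comment gets the right numbers but departs from the written derivation with no record of having done so.

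**Working it through.** **Inputs**

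- Formula, RR unit and rounding rule: Protocol 10.4.3, HR = 60/(RR × 1000), RR in msec, rounded to an integer.
- Unit of the output: Protocol 8.3.3 lists "Heart rate (bpm") among the vital signs, so beats per minute is the protocol's unit for heart rate.
- RR values: the documents give none. I assume 200 to 3000 msec, which corresponds to 300 down to 20 bpm and more than covers any plausible ECG.

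The protocol states no numerical heart rate, so there is no figure to reproduce. The check is a direct evaluation of the formula.

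**Step 1. As written, against the corrected form**

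| RR (msec) | 60/(RR × 1000) | Rounded | 60/(RR/1000) |
|---|---|---|---|
| 200 | 0.0003 | 0 | 300 |
| 600 | 0.0001 | 0 | 100 |
| 800 | 0.000075 | 0 | 75 |
| 1000 | 0.00006 | 0 | 60 |
| 1200 | 0.00005 | 0 | 50 |
| 3000 | 0.00002 | 0 | 20 |

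**Step 2. Size of the error.** The ratio of the correct to the written formula is [60/(RR/1000)] / [60/(RR × 1000)] = 1000 × 1000 = 1,000,000, whatever the RR. At RR 800 msec this is 75 against 0.000075.

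**Step 3. Does the choice of RR values matter?** For the written formula to reach 0.5, the smallest value that can round to 1, RR would have to be 60/(0.5 × 1000) = 0.12 msec. No ECG has such an interval, so the zero does not depend on the assumed range.

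**Step 4. Could only the unit label be wrong?** With RR in seconds, RR = 0.8 gives 60/(0.8 × 1000) = 0.075, which also rounds to 0. At RR = 0.2 seconds the result is 0.3, again 0 after rounding. Changing the unit does not repair the formula.

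**Step 5. What does repair it?** Either 60/(RR/1000) or, with the bracket moved, (60/RR) × 1000. Both equal 60000/RR with RR in msec and give the values in the last column.

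**Step 6. Does the error spread?** QTcF = QT/(RR/1000)^(1/3) takes RR directly and does not use heart rate. The QTcF values, their thresholds and the changes from baseline are therefore untouched.

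**The case against.** The arithmetic is hard to dispute. The case on the other side concerns consequence and certainty.

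- **The SAP may not use the formula.** SAP 8.2.1 refers to the central ECG read, and protocol section 10 leaves detailed methods to the SAP. If the central reader reports heart rate, the faulty derivation is never run. This is a fair reading, but the SAP does not settle it: the protocol has the central laboratory measure RR, PR, QRS and QT, and then calculates heart rate.
- **One use may have lapsed.** SAP 8.2.2 gives counts and percentages by QTcF category and does not repeat the protocol's outlier listing with heart rate. That stands. The summaries, changes from baseline and by-subject listing of changes remain in SAP 8.2.1.
- **Other safety outputs are intact.** QTcF does not depend on the formula, and heart rate is also measured as a vital sign (Protocol 8.3.3) and summarized with change from baseline in SAP 8.4. This stands in full.
- **The error would show itself.** A column of zeros would be caught at the first programming check, and the correct conversion a few lines below makes the intent clear. It is very unlikely to bias any conclusion.
- **The operator or bracket could be a fault in the PDF's electronic text.** This cannot be wholly excluded. It is unlikely, since the brackets and multiplication sign are explicit and the neighbouring RR/1000 reads correctly. The sponsor can check its source file.

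These points limit the consequence. None makes the formula correct.

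**Conclusion.** The concern holds: the derivation is wrong as written and gives 0 bpm for any recordable RR interval, an error of a factor of 1,000,000 before rounding. This rests on the formula reading in the sponsor's source file as it does in the public text; the RR values are illustrative and do not affect the result. The importance is minor. The primary endpoint, the QTcF analyses and vital-sign heart rate are all unaffected, and the error is likely to be noticed in programming. It is worth correcting because it is the only heart-rate derivation in the two documents and applies to a planned ECG safety variable.

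**What to change.** In Protocol 10.4.3, replace the formula with HR = 60/(RR/1000), equivalently 60000/RR, with RR in msec, and keep the rounding rule. In SAP 8.2.1, add one line stating either the same derivation or that heart rate is taken as reported by the central ECG reader. If the protocol is not to be amended, record the corrected formula in SAP section 12 as a change from the protocol.

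The cost is a one-character protocol correction and one SAP line. Nothing changes in design, data collection, sample size or patient management.

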10.4.4. Vital Signs

Descriptive summaries of vital signs measurements and changes from baseline will be generated.

10.5. Pharmacokinetic Analysis

Plasma concentrations of ESK-001 will be summarized descriptively by treatment group and time point.

10.6. Missing Data

Detailed missing data methodology will be described in the Statistical Analysis Plan.

10.7. Sample Size

The sample size is determined based on the primary efficacy endpoint. Calculations are based on a 1:1:1:1:1:1 randomization ratio (ESK-001 doses 1-5 vs. placebo) and will provide at least 99% power to detect 50% increase in the PASI-75 response rate in an active arm (i.e., 60% response rate) compared to the placebo assuming the response rate is 10% in the placebo arm. With a two-sided, two-sample test at a significance level of 0.05, a sample size of 35 patients per arm for a total of 210 patients is planned.

10.8. Interim Analyses

An independent SMC will be established to monitor safety data during the study. See [Section 9](#) for details.

11. ETHICAL, LEGAL, AND ADMINISTRATIVE ASPECTS

11.1. Data Quality Assurance

The overall procedure for quality assurance of clinical study data, including data collection and management, will be described in the Data Management Plan.

Accurate and reliable data collection will be assured by verification and cross-check of the eCRF against the Investigator's records by the study monitor (source document verification), and the maintenance of Drug Accountability by the Investigator. Monitoring details describing strategy, methods, responsibilities, and requirements, including handling of noncompliance issues and monitoring techniques are provided in the Monitoring Plan and contracts.

Electronic data capture (EDC) will be utilized. All patient data relating to the study will be entered by the study center from the source documents into the electronic case report forms (eCRFs) unless transmitted to the Sponsor or designee electronically (e.g., laboratory data). In no case is the eCRF to be considered as source data for the study.

Validation checks will be programmed within the EDC system to identify potential data discrepancies. Additionally, Sponsor personnel or designee will review the data entered by investigational staff for completeness and accuracy. If potential discrepancies are discovered, electronic data queries stating the nature of the potential discrepancy and requesting clarification will be sent to the site via the EDC system. Designated investigator site staff are required to respond promptly to queries and make necessary changes to the data. The sponsor assumes accountability for actions delegated to other individuals (e.g., contract research organizations)

For classification purposes, preferred terms will be assigned to the original terms recorded on the eCRF, using MedDRA for AEs, diseases and surgical and medical procedures, and the WHODrug dictionary for drug and herbal treatments.

11.2. Protocol Amendments and Study Completion

Protocol amendments must be made only with the prior approval of the Sponsor or its designees. The Institutional Review Board (IRB)/Independent Ethics Committee (IEC) must be informed of all amendments and give approval for all amendments. For studies conducted out of the US, approval of all substantial amendments must be obtained from the relevant Competent Regulatory Authority before implementation. The Investigator must send a copy of the approval letter from the IRB/IEC to the Sponsor and/or its designees.

Approval must be obtained before any changes can be implemented, except for Changes necessary to eliminate an immediate hazard to study patients, or when the change(s) involves only logistical or administrative aspects of the study (e.g., change in monitor, change of telephone number).

The Sponsor reserves the right to terminate the study, according to the Clinical Study Agreement.

Study completion is defined as the date when all patients have completed the final study visit, and the study database has been locked.

11.3. Informed Consent

The Investigator and Sponsor must agree upon the format and content of the informed consent for (ICF) before it is submitted to the IRB/IEC for approval. A copy of the IRB/IEC approved ICF will be forwarded to the Sponsor. Written IRB/IEC approved informed consent and Health Insurance Portability and Accountability Act (HIPAA) release (or other privacy protection release, as governed by local regulations) must be obtained from each patient before any study-related activities are conducted. The Investigator must retain all original signed and dated ICFs in the patient's file. A copy of the signed and dated ICF must be given to the patient.

The ICF documents the study-specific information the Investigator provides to the patient for the patient's agreement to participate. Among other things, the Investigator or his/her designee will fully explain in layman's terms the nature of the study, along with the aims, methods, anticipated benefits, potential risks, and any discomfort participation may entail. The ICF must be appropriately signed and dated before the patient enters the study.

Patients will be informed of findings from the earlier or concurrent clinical studies (including AEs), if it is considered that such information could potentially affect patients' willingness to participate or continue in the study. Depending on the nature, severity, and seriousness of these AEs, the ICF may be amended as deemed appropriate. All amended signed and dated ICF(s) must be retained in the patients' files at the study sites; and a copy must be given to the patient.

11.4. Data Handling and Record Keeping

11.4.1. Patient Confidentiality and Disclosure of Data

The Investigator must ensure that each patient's anonymity is maintained as described below. On the eCRFs or other documents submitted to the Sponsor and/or its designees, patients must only be identified by study, Patient Identification Number, and demographics, and pertinent restrictions of local regulations. No other personal identifies will be used, and data will be de-identified in a manner compliant with Privacy Laws and, for US patients, the HIPAA regulations. Documents that are not for submission to the Sponsor and/or its designee (e.g., signed ICFs and Patient Information Sheets) should be kept in strict confidence by the Investigator in compliance with Federal regulations or other applicable laws or ICF and GCP guidelines. The Investigation and institution must permit authorized representatives of the Sponsor and/or its designee, representatives of the FDA, national and local health authorities, and the IRB/IEC direct access to review the patients' original medical records for verification of study-related procedures and data. Direct access includes examining, analyzing, verifying and reproducing any records and reports that are needed for the evaluation of the study. The Investigation is obligated to inform the patient in the ICF that his/her study-related records will be reviewed, by the above-named representatives.

Patients will be informed that data will be held on file, by the Sponsor, and that these data may be viewed by staff including the study monitor and by external auditors on behalf of the Sponsor and appropriate regulatory authorities. Patients will also be informed that a study report will be prepared and may be submitted to regulatory authorities and for publication. However, patients will be identified in such reports only by Patient Identification Number and demographics,

pertinent to restrictions of local regulations. All patient data will be held in strict confidence, as allowed by law.

Upon the patient's permission, medical information may be given to the patient's personal physician or other appropriate medical personnel responsible for the patient's welfare.

